Demand for corticosteroid therapy such as hydrocortisone, dexamethasone and other corticosteroids due to inflammatory pulmonary disease;

Death;

Increase in white blood cell count (>10.000 cells/mm³);

Increase in C reactive protein test (CRP) (>3.00mg/L);

Deterioration of arterial blood gas paO₂/pFiO₂ ratio (<200);

Altered sodium (< 135mEq/L or > 145mEq/L);

Altered potassium (< 3,5mEq/L or > 5,5mEq/L);

Worsening of pulmonary area compromised (%) by inflammation or infection through tomographic assessment.

Method

EnHanCed study design

The present protocol refers to a phase I / II, prospective, randomized, parallel, triple blind clinical trial. This design is justified by the lack of a drug-specific cost-efficient treatment for SARS-CoV-2 patients. The use of a therapeutic drug justifies the need for a placebo control group. A minimum number of participants will be allocated to this study, as the main intention will be to evaluate the safety of the treatment. Triple blind clinical studies have the lowest levels of bias and, therefore, the highest level of evidence for a clinical study. It is understood that there is no need for a purely phase I study based on the literature data previously presented.

The study will be carried out at the São Paulo State University (UNESP) Clinical Hospital of the Botucatu Medical School, Botucatu, São Paulo, Brazil.

Dosage and administration

Considering the pulmonary water loss of 8 to 10mL during the gas exchange in 30 minutes (of inhalation) and compensating the dilution of the solution in the pulmonary fluids, we opted for the dose of 2.5 mg heparin in 10mL of 0.9% saline solution, aiming the effective mean tested doses (62.5 μ g/mL to 250 μ g/mL), nebulized 4/4 hours, except the nebulization that would be administered between 12 pm and 6 am. The treatment will be administered for 7 days because it will be assumed that the reduction in viral load promoted by enriched heparin will have a significant impact during the first 14 days of the infectious process. Considering that the patient has already had the disease for at least seven days when admitted and that the viral load tends to reduce spontaneously after the referred period, it is known that complications persist due to other factors such as inflammatory response.

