Individual vials containing 10 mL of enriched heparin (250 μ g/mL, that will be adjusted after the filtration process based on the result of biochemical analysis) or placebo (adding to the same total volume of 0.9% saline solution) will be prepared by the pharmacist, stored in a freezer at -30° Celsius, and delivered to the research team in a blind character. After receiving the preparation (enriched heparin or placebo), it must be inserted into the nebulizer cup and administered in a source of oxygen or compressed air (5L/min or according to the patient's need) in isolated rooms, a process that spend 30 minutes. Nebulization therapy will be performed after isolation of the patient and with support from the hospital infection control committee, so that there will be no greater risk of spreading the virus.

Eligibility criteria

Sign and agree to the free and informed consent form;

Both sexes, of any ethnic origin, aged between 18 and 90 years;

COVID-19 infected, diagnosed by reverse-transcriptase polymerase chain reaction (RT-PCR) or with a strong suspicion of COVID-19 through compatible clinical and radiological findings;

Time of disease evolution less than 10 days;

Radiological diagnosis of grade IIA pneumonia, with gas exchange ratio >200 in blood gas analysis (paO₂ / pFiO₂), characterizing mild hypoxemia;

Indication of hospital treatment regime, provided that the period of hospitalization before inclusion is not more than 24 hours;

Demand for supplemental oxygen therapy (O₂) less than 5 L/min.

Exclusion criteria

Disagree with the terms of the study;

Moderate or severe respiratory failure requiring ICU admission requiring invasive mechanical ventilation or positive pressure non-invasive ventilation (NIV);

Pregnancy or puerperium;

Hematological diseases;

Coagulation disorders;

Previous use of anticoagulants in therapeutic dosages for more than 72 hours;

Previous heparin-induced allergy or thrombocytopenia or current thrombocytopenia with a count of less than 50,000 platelets/mm³.

Discontinuation criteria

Participants can withdraw from the study, if they wish, at any time and regardless of the reason, without consent of the research team. Any type of severe adverse events, according to the rules of the Common Terminology Criteria for Adverse Events (CTC-AE 5.0)²⁵ will be considered criteria for discontinuation.

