The total recruitment size will be 50 participants, aiming at 40 patients followed during the study period. The sample was estimated considering the number of patients diagnosed as COVID-19 at the São Paulo State University (UNESP) Clinical Hospital that met the study's eligibility criteria.

The sample calculation of 40 patients took into account two independent study arms, with an estimated proportion in the viral load reduction rate of 30% for group 1, that will receive placebo, and 75% for group 2 that will be treated with enriched nebulized heparin as proposed in this study, considering 80% test power and a 5% significance level for a bilateral test.

Categorical variables will be evaluated with Fisher's exact test, continuous variables will be compared with non-parametric methods such as Mann-Whitney test or U test, paired comparisons will be evaluated with the Wilcoxon test, multivariate analyzes will be evaluated with regression Cox analysis and long-term clinical analyzes will be compiled on Kaplan-Meir curves.

Interventions and inpatient schedule

Intervention	Day 0	Day 1	Day 2	Day 3	Day 4	Day 5	Day 6	Day 7	Day 8
Informed consent form	X								
Medical visit, patient story and physical examination	X	X	X	X	X	X	X	X	X
Vital signs assessment	X	X	X	X	X	X	X	X	X
Medications in use	X	X	X	X	X	X	X	X	X
Inclusion and exclusion criteria	X								
COVID-19 viral load in RT-qPCR	X		X			X		X	X
Complete blood count, D-dimer, aPTT, urea, creatinine, glucose, reactive protein C, blood gas and amylase	X		X			X		X	X
Computed thoracic tomography	X								X
HMWH or placebo administration		X	X	X	X	X	X	X	X
Adverse events	X	X	X	X	X	X	X	X	X
Discontinuation criteria	X	X	X	X	X	X	X	X	

Table 1. Schedule for assessments and intervention. The participants will be followed up and evaluated on days 0, 1, 2, 3, 4, 5, 6, 7 and 8 days after randomization.

The closure assessment will be carried out on day 8. Extra data can be collected if the patient's clinical condition changes. Randomization will be performed in up to 24 hours after admission. After the end of the study, the participant will be referred and accompanied at the COVID-19 outpatient clinic São Paulo State University (UNESP) Clinical Hospital.

Adverse events

Adverse effects related to the nebulized use of heparins will be tracked and analyzed according to the Common Terminology Criteria for Adverse Events (CTC-AE 5.0),²⁵ and will be graded from 1 to 5, accordingly to the severity of the event.

Grade	Description

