Age (in years)					
Color (self-declared) (Brazilian Institute of Geography and Statistics terminology)³⁴	 White	 Black	 Indigenous	 Brown	 Asian
Residency	 Urban	 Rural			
Height (m)					
Weight (kg)					
Abdominal circumference (cm)					
Diabetes	 Yes	 No			
Hypertension	 Yes	 No			
Heart disease	 Yes	 No			
Dyslipidemia	 Yes	 No			
Obesity	 Yes	 No			
Sedentary lifestyle	 Yes	 No			
Smoking	 Yes	 No			
If smoker, smoking load (pack-year)					
Alcoholism	 Yes	 No			
Previous cardiovascular ischemic events	 Yes	 No			
Previous cerebrovascular ischemic events	 Yes	 No			
Previous venous thrombosis or pulmonary thromboembolism	 Yes	 No			
Neoplasia under treatment (<5 years)	 Yes	 No			
Acquired immunodeficiency syndrome	 Yes	 No			
Autoimmune disease	 Yes	 No			
Other diseases (report)					

Figure 1. Epidemiological and personal antecedents form based on Brazilian epidemiology.

Clinical assessment and physical examination form

Form Number:	Date:	
Diagnosis day		
Time elapsed since diagnosis (days)		
Time elapsed since start of treatment (days)		
Time elapsed since start of symptoms (days)		
Correct use of inhalation treatment	Yes 	No 
Symptomatic medications use	Yes 	No 
Supplementary oxygen use	Yes 	No 
Non-invasive ventilation use	Yes 	No 
Mechanical ventilation use	Yes 	No 
Bleeding	Yes 	No 
Type of bleeding (epistaxis, hematuria, upper / lower digestive hemorrhage, others)		
Bleeding start date (blank if not present)		
Bleeding end date (blank if still present)		

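### Disease day at entry may vary and may predict the fall in viral load, but no use of it is specified in the between-arm viral-load comparison

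*Combined protocol and SAP*

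**What the plan says.** Under Dosage and administration, the protocol assumes that the viral-load reduction from enriched heparin "will have a significant impact during the first 14 days of the infectious process". It adds that "the patient has already had the disease for at least seven days when admitted" and that load tends to decline by itself after that period. The entry rule, under Eligibility criteria, is "Time of disease evolution less than 10 days", with no lower limit.

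Table 1 takes quantitative viral load on Days 0, 2, 5, 7 and 8. The clinical assessment form has a field "Time elapsed since start of symptoms (days)", and the laboratory form records the viral load itself.

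Randomization is a single list of fifty positions, and no stratification factor is named. For between-arm comparisons the statistical paragraph names Fisher's exact test and the Mann-Whitney test. It also mentions multivariable Cox regression without naming covariates. No primary viral-load time point is given.

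**The concern.** The rationale and the entry rule describe different populations. The rationale has everyone at day 7 or later, when the load is already falling. The entry rule also admits patients in the first week. If both kinds enrol, the fall over a fixed study interval will depend partly on where each patient stood in the illness at entry. Day 0 load alone does not settle this, because the same load can be measured before the decline or during it.

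In a large trial this would be a minor loss of efficiency. With about 20 per arm it matters more. Variation in disease day adds noise to the treatment comparison, and a chance difference between arms can look like a drug effect or hide one. The variable that would remove much of this is already on the form, but the plan does not say that it will be used.

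**Working it through.** **Arm size.** The plan gives 40 followed, for 30% against 75%, two-sided 5%, 80% power. With pooled variance, n = [1.96·√(2·0.525·0.475) + 0.8416·√(0.30·0.70 + 0.75·0.25)]² / 0.45² = (1.384 + 0.531)² / 0.2025 = 18.1. That is 19 per arm, or 38 in all, consistent with 40. I use 20 per arm below.

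**Disease day at each swab** = entry day + study day, reading under 10 days as at most day 9:

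| Entry day | Day 0 | Day 2 | Day 5 | Day 7 | Day 8 |
|---|---|---|---|---|---|
| 6 | 6 | 8 | 11 | 13 | 14 |
| 7 | 7 | 9 | 12 | 14 | 15 |
| 8 | 8 | 10 | 13 | 15 | 16 |
| 9 | 9 | 11 | 14 | 16 | 17 |

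Days 2 and 5 fall by disease day 14 for every eligible patient. The Day 8 swab falls later for entry on days 7 to 9, and the Day 7 swab for entry on days 8 and 9. Entry on day 6 or earlier puts no swab past day 14.

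**Chance imbalance.** The documents give no distribution of entry days, so I assume uniform ranges. The SD of the between-arm difference in mean disease day is √(2·Var/20):

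- Days 2 to 9: Var = 5.25, SD = 0.72; a difference of 1 day or more in about 18% of trials.
- Days 5 to 9: Var = 2, SD = 0.45; about 3% of trials.
- Days 7 to 9: Var = 0.667, SD = 0.26; about 0.01% of trials.

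**Precision.** These inputs are assumptions, not figures from the documents: load flat to disease day 7, then a spontaneous fall of s = 0.2, 0.3 or 0.4 log10 per day, and residual SD 0.8 (variance 0.64). The outcome is the Day 0 to Day 5 change, chosen for illustration.

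Let m be the number of days of decline within that interval. For entry days 2 to 9, m = 0, 1, 2, 3, 4, 5, 5, 5, with variance 3.359. A straight line in entry day leaves 0.216 of this unexplained. For days 5 to 9, m = 3, 4, 5, 5, 5, with variance 0.64 and 0.14 unexplained. For days 7 to 9, m is always 5, so there is nothing to explain.

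Variance of the treatment estimate without disease day, relative to with it:

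ratio = (0.64 + s²·Var m) / (0.64 + s²·unexplained) × 35/36

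The factor 35/36 is the price of a second covariate at 40 patients, (37/36)/(37/35).

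| Entry days | s = 0.2 | s = 0.3 | s = 0.4 |
|---|---|---|---|
| 2 to 9 | 0.774/0.649 × 0.972 = 1.16 | 0.942/0.659 × 0.972 = 1.39 | 1.177/0.675 × 0.972 = 1.70 |
| 5 to 9 | 1.00 | 1.04 | 1.09 |
| 7 to 9 | 0.97 | 0.97 | 0.97 |

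Repeated simulations of this model adjust for Day 0 load in both analyses and assume a between-patient SD of 1.0 log10. They give 1.15 to 1.16, 1.39 to 1.43 and 1.65 to 1.73 for days 2 to 9. They give 1.00 to 1.11 for days 5 to 9 and 0.97 to 0.98 for days 7 to 9. A ratio of 1.16 is equivalent to about 16% more patients.

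**Size of an imbalance.** For entry over days 2 to 9, the slope of m on entry day is 4.0625/5.25 = 0.77. Unadjusted, a one-day difference in mean disease day therefore shifts the arm contrast by 0.77·s, or 0.15 to 0.31 log10. The ideal standard error of that contrast is 0.8·√(2/20) = 0.25.

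**The case against.** The strongest objection is that the gain depends on early entrants, whom the rationale says the trial will not have. Patients must also have pneumonia with mild hypoxemia and need hospital treatment, which makes very early entry less likely. If everyone enters on days 7 to 9, the covariate gains nothing and costs about 3%. This stands, and it is why the benefit is given as a range. It does not remove the point, because the entry rule sets no lower limit and the loss is small.

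Second, the randomized, blinded placebo arm already deals with spontaneous decline. This also stands: what remains is imprecision and chance imbalance. A reader might infer that natural clearance confounds the comparison; under this design it does not do so systematically.

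Third, a reader might infer from the swab table that the trial measures too late to test its own hypothesis. The documents do not support that. The 14-day sentence explains the length of treatment; it does not define an assessment window or say that the effect ends on day 15. Two post-baseline swabs lie within day 14 for every eligible patient, and nothing shows that a late swab decides efficacy. Nor do the documents say that both arms will have cleared by Day 8.

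Finally, the Cox model could include disease day, since its covariates are not named. So the fair statement is that no use is specified, not that use is excluded. Cox regression is in any case not a natural model for a change in viral load.

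**Conclusion.** The point holds as a low-cost gain in efficiency and robustness, not as a flaw that invalidates the trial. Disease phase at entry may vary under the entry rule and may predict the fall in load, yet no adjustment for it is specified.

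Under the assumed declines and residual SD, adjustment is worth about 16% to 70% more patients for entry over days 2 to 9, from almost nothing to 9% for days 5 to 9, and about a 3% loss for days 7 to 9. Which case applies depends on the entry days actually enrolled, which the documents do not give.

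The position of the Day 7 and Day 8 swabs beyond disease day 14 for later entrants is a caution for interpretation only. It also assumes that the clock for the infectious process and the clock for disease evolution are the same, which the protocol does not state.

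**What to change.** Specify the between-arm viral-load comparison as a baseline-adjusted model, for example ANCOVA on log10 load. Name Day 0 load and days since symptom onset at Day 0 as covariates before unblinding. The model can be applied at whichever swab day is named for efficacy.

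The cost is analysis-plan wording and one degree of freedom for disease day; both values are already on the forms. The sample size was built on a proportion, so the plan should say whether the adjusted comparison replaces the Fisher comparison or stands beside it.

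When late swabs are interpreted, note that Day 8 lies beyond disease day 14 for entry on days 7 to 9, and Day 7 does so for entry on days 8 and 9.

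Separately, the course length must be reconciled. The dosing text states "The treatment will be administered for 7 days", and the arm descriptions also give 7 days, but the Table 1 row "HMWH or placebo administration" is marked on Days 1 to 8. The swab arithmetic above does not depend on which is intended.

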A study carried out by Bendstrup, et al (2002),¹⁷ evaluated the effects of the inhibition of systemic coagulation through nebulized unfractionated heparin at doses up to 64 mg and identified that there is a dose-dependent effect for factor Xa inactivation, inducing minimal changes in aPTT, and it is safe for clinical or research purposes, without increasing the risk of bleeding.¹⁸

Phelps, et al (2020),¹⁹ carried out a systematic review on the use of UFH inhalation for the treatment of inhalation injury caused by heat in burn patients and concluded that nebulized heparin did not demonstrate an increase in the risk of bleeding rates and decreased the duration of mechanical ventilation.

For COVID-19, the heparin anti-viral effect is expected to be related to the fact that heparin blocks viral interaction with host receptors thereby inhibiting virus interaction with the cell and, consequently, viral invasion.^{20, 21} To this moment, some studies indicate that treatment with systemic heparin reduced hospital mortality in patients with COVID-19²² and a previous study that strongly supported the clinical investigation of heparin as a potential treatment for patients with COVID-19,^{23, 24} justifies further investigation to prove these clinical effects.

Objectives

Primary objectives assessment

Safety: related to the use of nebulized enriched heparin by patients with SARS-CoV-2 through the assessment of hemorrhagic events of any nature, alteration of the coagulation testing, like prolonged activated partial thromboplastin time (aPTT), indicated by an increase in aPTT>1.5, and heparin-induced thrombocytopenia; Efficacy: related to the proposed treatment, through analysis of the SARS-CoV-2 viral load of the participants treated by the sequential assessment of reverse transcription-polymerase chain reaction (RT-PCR) in the nasal swab.

Secondary objectives assessment

Safety measured by respiratory, clinical, laboratorial and tomographic findings as follows, in number of patients, and hospitalization days:

Supplemental oxygen therapy needed;

Mechanical pulmonary ventilation needed;

Renal failure development;

Development of major cardiovascular events such as pulmonary embolism and acute myocardial infarction;

Demand for intensive care unit (ICU) treatment;

Secondary pulmonary bacterial infections (bacterial pneumonia);

Deep vein thrombosis (DVT) through Doppler ultrasonography assessment;

Pancreatitis characterized by increase in amylase >200 U/L;

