Aphasia	Yes 	No 	
Aphasia start date (blank if not present)			
Aphasia end date (blank if still present)			
Hyporexia	Yes 	No 	
Hyporexia start date (blank if not present)			
Hyporexia end date (blank if still present)			
Heart rate (BPM)			

Brachial systolic pressure (mmHg)					
Brachial diastolic pressure (mmHg)					
Peripheral oxygen saturation (%)					
Axillary temperature (Celsius)					
Paleness	Normal 	1+/4+ 	2+/4+ 	3+/4+ 	4+/4+ 
Cyanosis	Normal 	1+/4+ 	2+/4+ 	3+/4+ 	4+/4+ 
Oral cavity	Normal 	Altered 			
Description					
Pulmonary auscultation	Normal 	Altered 			
Description					
Cardiac auscultation	Normal 	Altered 			
Description					
Abdominal examination	Normal 	Altered 			
Description					
Limbs (pulses, edema, skin conditions)	Normal 	Altered 			
Description					

Figure 2. Clinical assessment and physical examination form based on SARS-CoV-2 most prevalent symptoms.

Laboratory results and tomographic findings form			
Form Number:	Date:		
RT-qPCR	Positive 	Negative 	
RT-qPCR quantitative viral load			
Blood count	Normal 	Altered 	
Hemoglobin (g / dL)			
Hematocrit (%)			
Mean corpuscular volume (fL)			
Red cell distribution width (%)			
Platelets count (10³ / µL)			
White cell count (10³ / µL)			
Neutrophils (%)			
Lymphocytes (%)			
Bands (%)			
Arterial gas	Normal 	Altered 	
pH			
pCO₂ (mmHg)			
PaO₂ / FiO₂			
HCO₃ (mEq / L)			
SO₂ (%)			
Base Excess			
D-Dimer (µg / mL)			
aPTT	Normal 	Altered 	
Prothrombin time (PT)			
International normalized ratio (INR)			
Activated partial thromboplastin time (aPTT)			
Normalized aPTT Ratio			
Renal function	Normal 	Altered 	
Urea (mg / dL)			
Creatinine (mg / dL)			

Fasted glucose (mg / dL)	
C reactive protein (CRP) (mg / L)	
Amylase (U / L)	
Thoracic tomography description	

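### The primary aPTT safety event has no stated reference and need not be new after the first dose, so prolongation already present on Day 0 can count in either arm and dilute the comparison

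*Combined protocol and SAP*

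**What the plan says.** **Entry.** The Exclusion criteria list "Previous use of anticoagulants in therapeutic dosages for more than 72 hours" and, separately, "Coagulation disorders". The second carries no aPTT limit and does not say whether drug-induced prolongation is meant. The Eligibility criteria allow at most 24 hours in hospital before inclusion.

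**Endpoint.** Under Primary objectives assessment, safety rests on "assessment of hemorrhagic events of any nature", on a prolonged aPTT "indicated by an increase in aPTT>1.5", and on heparin-induced thrombocytopenia. For aPTT the text gives no unit or reference. For neither aPTT nor bleeding does it require onset after the first dose.

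**Data.** Table 1 schedules the blood panel ("Complete blood count, D-dimer, aPTT, urea, creatinine, glucose, reactive protein C, blood gas and amylase") on Days 0, 2, 5, 7 and 8, and "Medications in use" on every day from 0 to 8. The row "HMWH or placebo administration" starts on Day 1, so the Day 0 aPTT precedes treatment. The laboratory form (Figure 3) has a field "Normalized aPTT Ratio". The clinical form (Figure 2) records the date a bleed began.

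**Analysis.** The statistical section assigns Fisher's exact test to categorical variables and Mann-Whitney to continuous ones, with Wilcoxon for paired comparisons and Cox regression for multivariate work. None of these is tied to aPTT or to a Day 0 value.

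**The concern.** A patient started on therapeutic anticoagulation at admission has had at most 24 hours of hospital treatment at inclusion. The 72-hour rule does not exclude that patient, who may have a raised aPTT before any study nebulization.

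If the endpoint is a fixed cut-off, that patient can be an event whichever arm is assigned. Such events say nothing about the study drug. They raise the event rate in both arms, shrink the difference between them, and can fall unevenly in a small trial. The protocol describes the evaluation of safety as the trial's main purpose and expects little systemic absorption by inhalation, so any real aPTT signal may be small and easily masked. The pre-dose measurement that would remove this noise is already scheduled, but the endpoint and the tests do not use it.

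**Working it through.** **1. The plan's own figure.** The documents give no calculation for the safety endpoints. The only calculated figure is 40 patients for viral load (30% against 75%, 80% power, two-sided 5%). With mean proportion 0.525:

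n per arm = [1.96·√(2·0.525·0.475) + 0.842·√(0.30·0.70 + 0.75·0.25)]² / 0.45² = (1.384 + 0.531)² / 0.2025 ≈ 18.1, so 19 per arm and 38 in total.

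That is close to 40, and 40 / 0.80 = 50 recruits. Hence 20 to 25 per arm below.

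**2. How the endpoint reads.** The secondary objectives use the same form of words for amylase above 200 U/L, white cells above 10.000 per mm³ and CRP above 3.00 mg/L. All are fixed cut-offs. By that pattern, and given the normalised-ratio field on the laboratory form, 1.5 is most naturally a fixed ratio. A change from baseline remains a possible reading.

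**3. Model (all rates assumed).** Let b be the share of each arm already above 1.5 on Day 0, and e the share of the remaining heparin patients pushed above 1.5 by study drug. Placebo patients have no new events.

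- Fixed cut-off: placebo rate b, heparin rate b + (1 − b)·e, 25 per arm.
- New events only: 0 against e, among the 25·(1 − b) per arm at risk, rounded down to 25, 22, 20 and 17.

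Exact power of the two-sided 5% Fisher test:

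| b | e = 30%, fixed | e = 30%, new only | e = 10%, fixed | e = 10%, new only |
|---|---|---|---|---|
| 0% | 81% | 81% | 3.3% | 3.3% |
| 10% | 50% (10% v 37%) | 84% | 7.1% (10% v 19%) | 6.2% |
| 20% | 33% (20% v 44%) | 76% | 5.2% (20% v 28%) | 4.3% |
| 30% | 26% (30% v 51%) | 61% | 4.5% (30% v 37%) | 2.2% |

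The new-event figures can be checked by hand. With no placebo events, Fisher rejects at 6 or more heparin events out of 25, and at 5 or more out of 22, 20 or 17. For e = 30%, P(X ≥ 6 of 25) = 0.807 and P(X ≥ 5 of 22) = 0.835. The rise from 81% to 84% therefore comes from the discreteness of the test and is no real gain.

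**4. Some new events on placebo.** With 5% on placebo against 30% on heparin, for b = 0, 10, 20 and 30%:

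- 25 per arm: fixed 55, 32, 23, 18%; new only 55, 51, 45, 35%.
- 20 per arm: fixed 45, 26, 18, 12%; new only 45, 38, 31, 24%.

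**5. False positives.** With no drug effect and the same b in both arms, Fisher's type I error at 25 per arm is 0.9%, 2.2% and 2.3% for b = 10%, 20% and 30%, all below 5%.

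**6. Chance imbalance.** With 20 per arm, the arms differ by three or more patients already prolonged on Day 0 with probability 18%, 32% and 39% for b = 10%, 20% and 30%.

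**The case against.** The strongest reply has five parts.

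- **A baseline exists, and the wording can be read as change from it.** This is partly right. Day 0 aPTT is scheduled before dosing, so the gap lies in the endpoint definition and not in the data. But the same wording is used elsewhere for fixed cut-offs, and no test is tied to Day 0.
- **Attribution is not automatic.** The Adverse events section calls for the causal link to enriched heparin to be considered. A reader might infer that the plan charges pre-existing prolongation to the study drug, and the documents do not say so. However, causality review is described for adverse events. The aPTT value sits on the laboratory form and is not a listed item on the adverse event form, so this review does not settle how the endpoint is counted.
- **The placebo arm protects the comparison.** This stands as regards false positives. A reader might infer that background prolongation could create a heparin signal. In expectation it raises both arms alike, and the test already allows for chance imbalance. What remains is lost power and noise.
- **The power gain rests on an assumed large effect.** This stands. The protocol's Inhaled Heparin section cites little change in aPTT at inhaled doses up to 64 mg, against 2.5 mg per nebulization here. At a 10% effect neither definition has useful power, and counting new events gains nothing in the Fisher test.
- **Bleeding is separable.** This also stands, because the start date is recorded. The plan only lacks the rule to use it, and no size is claimed for bleeding.

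**Conclusion.** The point holds in a limited form. A primary safety endpoint has no stated reference and no requirement of onset after the first dose, while the entry rules admit patients whose aPTT may already be raised. On the fixed-cut-off reading, such patients can count in either arm.

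The consequence is dilution and added noise without an inflated error rate. Its size cannot be fixed from the documents, which give neither the rate of therapeutic anticoagulation at entry nor that of a Day 0 ratio above 1.5. With an assumed 30% drug effect, 10% to 30% background and no new placebo events, power at 25 per arm is 50% to 26% on the fixed cut-off and 84% to 61% for new events. With an assumed 10% effect it is below 8% under both. The case for the change therefore rests on a clear, interpretable endpoint and on use of the baseline value, more than on any promised power.

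One further inference should be resisted: that patients given anticoagulants during the trial should be excluded or adjusted for. Deep vein thrombosis and pulmonary embolism are themselves trial outcomes and could prompt such treatment. Conditioning on it would break the randomised comparison.

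**What to change.** 1. **Event definition.** Define the aPTT event as a normalised ratio at or below 1.5 on Day 0 and above 1.5 at any scheduled or extra measurement after the first dose. Count as primary bleeding events only those with a start date after the first dose.
2. **Continuous analysis.** Analyse the aPTT ratio as a continuous outcome adjusted for its Day 0 value, in place of an unadjusted Mann-Whitney comparison. Name in advance which post-dose value is used.
3. **Anticoagulant use.** Tabulate Day 0 aPTT and systemic anticoagulant use by arm from the medication record. Limit any adjusted or subgroup analysis to use at Day 0. Report use started after randomisation descriptively only. The new-event definition does not remove prolongation caused by such later use, so this table is needed to read the result.

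**Cost.** Wording in the analysis section, made before unblinding. All inputs are already in Table 1 and the case forms. Eligibility, visits and sample size do not change. The one downside is that patients above 1.5 on Day 0 leave the denominator of the binary aPTT event and inform only the continuous analysis. Their number should be reported by arm.
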